Appendix 3. Radiographic evaluation of adenoid size:

Radiographic evaluation of adenoid size by the method of Cohen and Konak (1). Thickness (mm) of "Airway column" (A) and "Soft palate" (B) is measured and A/B ratio is calculated in order to evaluate nasopharyngial airway patency.

Lateral neck radiographs will taken and interpreted by the method of Cohen and Konak by a blinded radiologis (1). According to this method, the thickness of the soft palate (SP) in its superior anterior part and the airway column (AC) immediately posterior to it will measured and AC/SP ratio

was calculated. The measurement will done about 1 cm below the upper end of the soft palate in children > 3 years of age and half a centimetre in younger children. A radiographic example of this method is demonstrated in Figure 1.

Degree of obstruction was graded as follows: AC/SP ≥1 (grade 0 or no obstruction), AC/SP= 0.50-0.99 (grade 1 or mild obstruction), AC/SP= 0.01-0.49 (grade 2 or severe obstruction), AC/SP= 0 (grade 3 or total obstruction).

Flexible nasopharyngoscope:

Topical anesthesia will use in the form of a mixture of lidocaine/ neosynephrine spray that will applied by pressurized nozzle prior to endoscopic examination. The patient will be seated upright in the examination chair without restraint during the exam. A standard 4.0 mm flexible nasopharyngoscope with attached fiberoptic light will be used to perform the nasopharyngoscopy. The data will be recorded as a perceived percent obstruction of the choana by the adenoid pad, as seen through the endoscope.

Lertsburapa K, SchroederJW, Sullivan c. Assessment of adenoid size: A comparison of lateral radiographic measurements, radiologist assessment, and nasal endoscopyInternational Journal of Pediatric Otorhinolaryngology 74 (2010) 1281–1285

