Every 3 months patients will be asked to come to the clinic and all their records will be collected and they will be evaluated by the ENT specialist for the adenoid tissue size. All these parameters will be recorded in specific forms by the investigator (Table 5).

Patients will be allowed to use nasal corticosteroids, antihistaminic drugs and flu vaccine during the study period and all these study medications will be recorded.

At the end of the study (12 months), immunoglobulin levels will be measured to compare them with basal level.

	1				
Sample Size	A total of 68 patients will be randomized in the study in a 1:1 ratio				
	to Active or Placebo groups.				
	Active group: 34 patients				
	Placebo group: 34 patients				
N ^o Sites					
	Number of study centers: 1				
	Study center: [name] Maternity and Children Research and				
	Training Hospital, Department of Pediatric Allergy and				
	Immunology, Ankara, TURKEY.				
	Study Coordinator and Principal Investigator:				
	[name] M.D. Associate Prof. of Pediatrics and Pediatric				
	Allergy, Training staff on Pediatric Allergy				
	Other Investigators:				
	[name] M.D. Professor of Pediatrics & Subspecialist on				
	Pediatric Allergy and Pediatric Pulmonology				
	Chief of Pediatric Allergy and Immunology Department				
	[name] M.D. Otolaryngologist				
	[name] M.D. Radiologist				
	Statistical method:				
Statistical Methods	All analyses will performed with a commercially available software				
	program (SPSS Statistical Software, version 11.5; SPSS, Inc,				
	Chicago,Ill).				
	The Shapiro-Wilks test will use to evaluate normality of the				
	distributions collected. When variables were normally distributed,				
	they were expressed as means (SDs); otherwise, they will express as				
	medians and interquartile ranges (25th-75th percentiles). The x^2 test				
	will use for categorical variables and expressed as observation				
	counts (in percentages). An ANOVA (or Mann-Whitney U				
	depending on the normality of data) statistics will be used to				
	compare means between both treatment groups for continuous				
	variables. Bonferroni multiple comparison test will use to compared				
	paired intervals (0-3, 0-6 months). All P values are 2-tailed; a P				
	pared intervals (0.5, 0.0 inontins). An 1 values are 2-tailed, a 1				

	value of loss than 05 are considered statistically significant					
	value of less than .05 are considered statistically significant.					

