	Sample Size:					
	In one study OM-85 group showed 3 less RTIs compared with					
	placebo over 12 months period. A sample size of 54 randomized					
	patients (27 per group) will provide at least 80% power to detect a					
	mean difference of at least 2.0 RTIs between the two groups					
	assuming a SD of 2.55 and assuming a drop-rate of 20% after 6					
	months, total of 68 patients (34 per group) will recruit to the study. ¹					
	Reference:					
	1. María Dolores Gutiérrez-Tarango and Arturo Berber. Safety and Efficacy of Two Courses of OM-85 BV in the Prevention of Respiratory Tract Infections in Children During 12 Months.					
	CHEST 2001; 119:1742–1748					
Planned Timelines	Planned date first patient consented/enrolled/observed: 01					
	September 2017					
	Planned date last patient consented/ enrolled/ observed: 01 March					
	2018					
	Planned date last patient last observation/ treatment: 01 March 2019					
	Planned date CSR (Clinical study report) available: June 2019					

1. Visit	2. Visit	3. Visit	4. Visit	5. Visit	6. Visit
Randomitaz ion of the patients	After randomization treatment plan (OM-85 capsules or placebo given in the first 10 days of each month for 3 months)	Control at the end of 3rd month of treatment (20 days after the last medicine/drug or placebo)	Control after 3 months of last drug or placebo intake and Given the product by the previous randomization again for 3 months	At the end of the second 3-month treatment (20 days after the last drug)	Control after 3 months of the last drug or placebo intake (20 days after the last medicine/drug or placebo)

• Patients will be assessed for type of respiratory infection and additional treatment by researchers (pediatric allergy specialists and/or ENT specialists) in the Pediatric Allergy and Immunology outpatient clinic when symptoms of respiratory tract infection is present.

- Parents will be asked to fill in the relevant form [Symptom Score Form] during this acute respiratory tract infection.
- Every 3 months, parents will be filled.QoLQ "Tonsil and Adenoid Health Status Survey".

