Please answer these questions remembering the past 6 months for your child. The questions relate to the problems many children have related to their tonsils and adenoids. If a certain question is not a problem for your child, please circle "0" (not a problem) for that question. Please do not skip questions or leave any questions unanswered.

.....

Over the past 6 months, how much of a problem were the following conditions for your child?

Please circle the most correct response

		Nict a problem	very mild problem		fairly bad problem	severe problem	
1.	Snoring loudly during sleep	0	1	2	3	4	1
2.	Strep throat infections	0	1	2	3	4	2
3.	Many trips to a doctor's office	0	1	2	3	4	3
4.	Taking antibiotics for more than 3 weeks straight	0	1	2	3	4	4
5.	Taking antibiotics over and over for less than 2 weeks at a time	0	1	2	3	4	5
6.	Many calls to a doctor's office	D	1	2	3	4	8
7.	Irregular or stopped breathing, also known as apnea, during sleep	D	1	2	3	4	,
8.	Repeated short-term (or acute) infections of the tonsils that last less than 2 weeks	D	1	2	3	4	a
9.	Constant, or chronic, infection of the tonsils that last more than 2 weeks	D	1	2	3	4	9
0.	The cost of medical care and prescriptions	D	1	2	3	4	16
1.	Breathing through the mouth during the day	0	1	2	з	4	11
2.	Your child not growing or gaining weight as expected	0	1	2	з	4	12
13.	Noisy breathing during the day	D	1	2	3	4	12
4.	Problems with poor appetite or poor eating habits	0	1	2	3	4	14
5.	Behavior problems at home or at school, or poor school grades or reports	0	1	2	3	4	11

Table 5. Follow-up form

Visit (3-6-9-12 months)	Date:					
Number of RTIs in previous 3 months:						
• Туре	AOM	AS	AT	AN	AC	Р

Number					
Duration (days)					
Antibiotic use in previous 3 months					
• Туре					
Number (box)					
Duration (days)					
Hospitalisation:	(((($\overline{(0)}$	$\overline{(1111)}$	(((($\overline{(00)}$
Number					
Duration (days)					
Symptome score					
QoLQ (Score)					
Adenoid size					
Radiological (AC/SP ratio)					
 Nasopharingoscope (perceived percent obstruction of the choana) 					

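### The endoscopic adenoid score is a subjective estimate, and nothing keeps its scorer from knowing the child's infection history, which treatment blinding does not hide.

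*Protocol*

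**What the plan says.** The Endpoints section of the protocol lists adenoid size over 12 months as a secondary endpoint, assessed by radiograph and by flexible nasopharyngoscopy.

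- **Radiograph.** Appendix 3 has the films interpreted "by a blinded radiologis" (the word is cut short in the source).
- **Endoscopy.** The flexible nasopharyngoscope part of the same appendix says "The data will be recorded as a perceived percent obstruction of the choana by the adenoid pad, as seen through the endoscope". It names no blinded, independent or second reader.
- **Who scores, and when.** Under Procedures, at each 3-monthly clinic visit "all their records will be collected and they will be evaluated by the ENT specialist for the adenoid tissue size".
- **Who diagnoses RTIs.** The notes under the visit table say "Patients will be assessed for type of respiratory infection and additional treatment by researchers (pediatric allergy specialists and/or ENT specialists").
- **Staffing.** The sites section gives "Number of study centers: 1" and lists a single "M.D. Otolaryngologist".
- **Form.** Procedures continues "All these parameters will be recorded in specific forms by the investigator (Table 5"). In Appendix 1, Table 5 opens with "Number of RTIs in previous 3 months" and carries both adenoid measures at its foot.

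The Design section makes the trial double-blind with matching placebo. The Rationale says adenoid tissue is expected to shrink because there will be fewer inflammatory RTIs.

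**The concern.** Blinding to treatment keeps the endoscopist from scoring by arm. It does not keep the endoscopist from scoring by infection history. If OM-85 works on the primary endpoint, history differs between arms. Any influence of known history on an eyeballed percentage then becomes a difference between arms. The protocol states the expected direction, so a scorer who knows that a child had few infections also knows what the hypothesis predicts for that child's adenoid.

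The research question is whether fewer infections lead to smaller adenoids. A score coloured by the infection count would make that link partly circular on the endoscopic measure. The problem would arise in the scenario where a size claim is most likely to be made, namely when RTIs have fallen. A live estimate that was not recorded cannot be re-read later by someone unaware of the history.

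**Working it through.** **1. What the text permits.** Three facts are set side by side.

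- The adenoid scorer is the ENT specialist (Procedures).
- RTIs may be assessed by allergy specialists, ENT specialists or both (notes under the visit table). With one otolaryngologist listed at one centre, an RTI assessed by ENT would, on the listed staffing, be assessed by the person who scores the adenoid.
- RTI records are gathered at the visit where the adenoid is scored, and both end up on Table 5.

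No text separates the roles or withholds the records from the scorer.

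**2. The plan's own figure.** The Sample Size section uses a difference of 2.0 RTIs, SD 2.55 and 27 per group. For a two-sample t-test at two-sided 0.05, the noncentrality is 2.0 / (2.55 × √(2/27)) = 2.88, which gives 80.7% power. Also 54 / 0.8 = 67.5, rounded up to 68. Both planned figures reproduce. They are used below only as inputs.

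**3. Illustration of the bias.** From the documents: n = 27 per arm, planned RTI difference 2.0, two-sided 0.05. Assumed, because the documents give neither: the SD of the percent score is 20 points (range 15 to 25), and the score rises by b = 1, 2 or 3 points per RTI known to the scorer. There is taken to be no true difference in adenoid size.

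- Spurious arm difference: δ = b × (difference in RTIs known to the scorer)
- Noncentrality: λ = δ / (SD × √(2/27)). At SD 20 the denominator is 5.44.
- Rejection probability: noncentral t with 52 degrees of freedom, critical value 2.007. With two groups, the planned ANOVA is this same test.

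*Scorer knows the full 12-month difference (2.0 RTIs):*

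| b | δ (points) | λ at SD 20 | Rejection, SD 20 | SD 25 to SD 15 |
|---|---|---|---|---|
| 1 | 2 | 0.37 | 6.5% | 6.0% to 7.7% |
| 2 | 4 | 0.73 | 11.1% | 8.9% to 16.1% |
| 3 | 6 | 1.10 | 19.1% | 13.9% to 30.3% |

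*Scorer knows only the 3-month count on Table 5.* Spreading the 2.0 evenly over four visits (a further assumption) gives 2.0 / 4 = 0.5 RTI per sheet:

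| b | δ (points) | λ at SD 20 | Rejection, SD 20 |
|---|---|---|---|
| 1 | 0.5 | 0.09 | 5.1% |
| 2 | 1.0 | 0.18 | 5.4% |
| 3 | 1.5 | 0.28 | 5.8% |

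**4. Sensitivity.** If the assumed SD excludes the scorer's influence, the total SD is √(SD² + (b × 2.55)²). At SD 20 and b = 3 this is √(400 + 58.5) = 21.4. The 12-month rates at SD 20 become 6.5%, 10.8% and 17.3%. At SD 15 and b = 3, 30.3% falls to 25.0%.

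**5. Boundary case.** If the arms do not differ in RTIs, δ = 0 for every b and the rate is 5%.

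**The case against.** The main safeguard is in place: allocation is random and treatment is blinded with matching placebo. What remains is an indirect path with three links: a real RTI difference between arms, a scorer who knows each child's history, and a scorer influenced by it. The documents show only that the second is possible. This stands, and it makes every rate above conditional.

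A reader might infer that the protocol has the records opened before the endoscopy. It does not say so. Procedures joins two events of one visit with a plain conjunction, and field order on a form is not order of work. Table 5 is completed by the investigator, not expressly by the ENT specialist. It also holds the radiological ratio, which a separate radiologist reads, so sharing a sheet does not show that a scorer sees the counts. What survives is that the plan sets no order, so either order complies.

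A reader might also infer that the same person routinely diagnoses RTIs and scores adenoids. The wording allows ENT involvement without requiring it, and RTI assessment takes place in the allergy clinic. The overlap is permitted, not established.

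The SD and the points per RTI have no source in the documents, and the larger rates need the scorer to carry the full 12-month difference in mind. That also stands.

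Finally, the stakes are limited. Endoscopy is one of two measures of one secondary endpoint, the other measure has a blinded reader, and the primary RTI count is unaffected.

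**Conclusion.** The gap is real but modest. The plan leaves a subjective, live adenoid score open to knowledge of infection history, and treatment blinding does not close that route. If OM-85 lowers RTIs, a scorer swayed by that history could create or enlarge a size difference between arms on endoscopy.

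The documents do not support saying that this will happen or how large it would be. On the stated assumptions (SD 20, 27 per arm, 1 to 3 points per known RTI, no true size effect), the conditional false-positive rate runs from about 5% to 6% with only the 3-month count known, and from 6.5% to 19% with the full 12-month difference of 2.0 RTIs known. Neither range is an unconditional error rate for the trial.

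The change is worth making because it costs almost nothing and must be made before the scores are taken.

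**What to change.** In Procedures and with Table 5, state that at each 3-monthly visit the endoscopy is done and the percent obstruction is written on a separate sheet before that visit's RTI records are collected, opened or discussed. Add a field flagging visits where the scorer had also diagnosed an RTI in that child, and report the number of flagged visits by arm. Flagged visits should not simply be dropped from the comparison, because having had an RTI diagnosed is itself an outcome after randomisation.

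The cost is one extra sheet and a fixed visit order. No additional visit, reader, procedure or patient is needed, and the sample size does not change. The bias is reduced but not removed: a scorer may remember earlier infections or notice current symptoms.

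Two further steps are not needed. Taking RTI diagnosis away from ENT could weaken the primary endpoint, because Appendix 2 defines otitis by pneumatic otoscopy and tonsillitis by tonsillar findings. Making an endoscopic claim depend on the direction of the AC/SP ratio is a choice of endpoint hierarchy that this concern does not require.

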Statistical method:

All analyses will be performed with a commercially available software program (SPSS Statistical Software, version 11.5; SPSS, Inc, Chicago, Ill). The Shapiro-Wilks test will be used to evaluate normality of the distributions collected. When variables were normally distributed, they were expressed as means (SDs); otherwise, they will be expressed as medians and interquartile ranges (25th-75th percentiles). The χ^2 test will be used for categorical variables and expressed as observation counts (in percentages). An ANOVA (or Mann-Whitney U depending on the normality of data) statistics will be used to compare means between both treatment groups for continuous variables. Bonferroni multiple comparison test will be used to compare paired intervals (0-3, 0-6 months). All P values are 2-tailed; a P value of less than .05 are considered statistically significant.

Sample Size:

In one study OM-85 group showed 3 less RTIs compared with placebo over 12 months period. A sample size of 54 randomized patients (27 per group) will provide at least 80% power to detect a mean difference of at least 2.0 RTIs between the two groups assuming a SD of 2.55 and assuming a drop-rate of 20% after 6 months, total of 68 patients (34 per group) will be recruited to the study.¹

Reference:

María Dolores Gutiérrez-Tarango and Arturo Berber. Safety and Efficacy of Two Courses of OM-85 BV in the Prevention of Respiratory Tract Infections in Children During 12 Months. CHEST 2001; 119:1742–1748

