	gamma globulins, or anticonvulsive drugs within the				
	previous 6 months.				
Endpoints	Primary Endpoint: Cumulative number of RTIs over the 12				
	months.				
	monuis.				
	Secondary Endpoints:				
	• Duration in days of RTIs				
	• Antibiotic use (n. of cycles and days)				
	Missed school/work days				
	• Adenoid and tonsil survey (described in appendix 1 of the				
	original protocol)				
	• Size of adenoid tissue over the 12 months according to				
	radiographic and flexible nasopharyngoscopic evaluation (described				
	in appendix 3 of original protocol).				
	Surgery need				
	• AEs				
	Patients will be recruited from 01 September 2017 to 01 March				
Procedures	2018. The trial will begin in 01 September 2017 and will be				
	completed 01 March 2019.				
	Children with the ages of 2-6 years who have recurrent RTIs and				
	AH will be evaluated for the eligibility for the study. When eligible				
	for the study, children's all demographic characteristics will be				
	recorded (Table 1). Eligible children will be evaluated by ear-nose-				
	throat (ENT) specialist and flexible laryngoscopy and radiographic				
	evaluation of adenoid size will be performed in order to measure the				
	adenoid size. All children will be evaluated by an allergy specialist.				
	Complete blood count, serum IgG, IgA, IgE, IgM will be measured.				

Skin prick test will be performed with common allergens.

All children will be randomized into two study arms (active treatment and placebo). OM-85 3.5 mg capsule or placebo will be given according to the standard treatment schedule (10-10-10) for the three consecutive months. All patients will receive 2 cures of treatment at the beginning and 6 Months after inclusion in the study. Every patients will be followed-up for 12 months.

Patients (and care giver/parents) will be given a symptom score form (Table 2) in order to record all nasal symptoms, signs and duration of RTIs, antibiotic use, days of absenteeism from school and from work for family members, monthly.

All patients will be asked to come to the clinic when they have symptoms of RTI in order to diagnose the type of RTIs. Then they will be asked to complete the infection form during the acute RTIs (Table 3).

Every 3 months they will fill in the Tonsil and Adenoid Health Status Survey (Table 4).

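### The primary RTI count has no analysis of its own: a normality test picks the test and the summary, and neither route plans an effect estimate or confidence interval for the mean difference the trial is sized on.

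*SAP*

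**What the plan says.** The primary endpoint is a count per child (Protocol, Endpoints): "Primary Endpoint: Cumulative number of RTIs over the 12" months. Neither document gives it a dedicated analysis. One rule in the SAP under Statistical method, repeated in substance in the Protocol under Statistical Methods, serves every continuous variable:

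- The gate: "The Shapiro-Wilks test will be used to evaluate normality of the distributions collected".
- The summary: means (SDs) if normal; "otherwise, they will be expressed as medians and interquartile ranges (25th-75th percentiles").
- The test: "An ANOVA (or Mann-Whitney U depending on the normality of data) statistics will be used to compare means between both treatment groups".
- The only inferential output: "All P values are 2-tailed; a P value of less than .05 are considered statistically significant".

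The sample size paragraph works on another footing. It plans 27 per group "to detect a mean difference of at least 2.0 RTIs between the two groups", with SD 2.55, raised to 34 per group for 20% dropout. No mean difference, rate ratio, shift estimate or confidence interval is named for any endpoint.

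**The concern.** The sample size fixes the quantity of interest as the difference in mean RTIs per child over a year. The analysis text lets the collected data decide whether that quantity is reported. If Shapiro-Wilk rejects, the planned report for the primary endpoint is two medians, two interquartile ranges and a P value. A mean difference and its interval cannot be worked back from those without further assumptions. Mann-Whitney U assesses whether one arm's counts tend to be larger than the other's, so the SAP's statement that it compares means is wrong for that branch.

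The rule is also incomplete. It does not say whether normality is tested in each arm, in the pooled data or on residuals, and that choice changes how often the switch occurs.

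At stake is the main number of a 68-child trial: how many infections per child are avoided, and with what precision.

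**Working it through.** **1. The plan's own figure.** Inputs from SAP, Sample Size: difference 2.0, SD 2.55, two-sided 0.05, 80% power.

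- Normal approximation: n = 2(1.960 + 0.842)² × (2.55/2.0)² = 25.5, so 26 per arm.
- Two-sample t-test: 26.5, so 27 per arm, with power 80.7%.
- Dropout: 54/0.80 = 67.5, so 68.

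The stated 27, 54 and 68 reproduce. They are calculated for a comparison of means.

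**2. How often would the rule switch to ranks?** The plan states no expected arm means, so these are assumptions shown as a range.

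- *5.57 vs 3.57.* The Protocol Introduction cites a pooled reduction of 35.9%. With a difference of 2.0, the placebo mean is 2.0/0.359 = 5.57 and the active mean 3.57. Counts are negative binomial with average variance 2.55² = 6.50, so the dispersion is (6.50 − 4.57)/[(5.57² + 3.57²)/2] = 0.088.
- *6 vs 4.* Same average variance: dispersion (6.50 − 5)/[(6² + 4²)/2] = 0.058.
- *8 vs 6.* Either dispersion 0.1 (SDs 3.79 and 3.10) or Poisson (SDs 2.83 and 2.45).

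Share of simulated trials in which Shapiro-Wilk gives P < 0.05, shown as tested in either arm / pooled:

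| Means | 27 per arm | 34 per arm |
|---|---|---|
| 5.57 vs 3.57, average SD 2.55 | 61% / 82% | 74% / 93% |
| 6 vs 4, average SD 2.55 | 53% / 71% | 66% / 86% |
| 8 vs 6, overdispersed | 48% / 63% | 59% / 77% |
| 8 vs 6, Poisson | 32% / 38% | 41% / 51% |

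These are simulation figures, accurate to a point or two. With 8 vs 6 and SD 2.55 in both arms the range is 16% to 38% over both sample sizes and three ways of applying the test. That scenario needs a placebo count less variable than Poisson, since 6.50 < 8.

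**3. What the summaries would convey.** At 27 per arm the mean difference has standard error 2.55 × √(2/27) = 0.69 (0.68 to 0.70 in simulation). If a reader subtracts the two reported medians, that contrast has SD about 0.94. The variance ratio is (0.94/0.70)² = 1.8, or about 1.9 with the lower simulated values (0.93 and 0.68).

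**4. Error rate and power.** At 5.57 vs 3.57 and 27 per arm, power is 0.82 for Welch and 0.81 for the two-stage rule. Across separate simulations the null error of the two-stage rule was 4.7% to 5.6%, against 4.9% for Welch.

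**5. The interval the plan could report.** On the plan's inputs the 95% half-width is 2.007 × 0.694 = 1.39 RTIs at 27 per arm. At 34 per arm it is 1.997 × 2.55 × √(2/34) = 1.23.

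**The case against.** The strongest reply is that the rule is written in advance, keeps its type I error and costs no power, so nothing false would be concluded. That stands: this is not a validity problem. Several stronger readings are tempting, and the documents do not support them.

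- *The switch to medians is likely.* It is better than even in many scenarios but not in all. Entry requires at least 3 RTIs in 6 months, and the reference study reported 3 fewer RTIs over 12 months. Both are compatible with higher means, at which the switch becomes less frequent.
- *The test is picked with treatment codes open.* The SAP says nothing about codes, and a pooled normality test need not use allocation.
- *The switch causes the missing interval.* The ANOVA route plans none either. The difference is that means and SDs allow one to be derived, whereas medians and interquartile ranges do not.
- *The medians would badly mis-state the benefit.* The SAP plans medians as description, not their difference as an estimate. Counting median differences of 1 or less, or 3 or more, gives 57% of trials against 14% to 16% for means. This comes from whole-number medians falling exactly on 1 or 3. With strict cut-offs it is about 10% against 13% to 15%. Only the ratio of variances is a sound comparison.

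One further point favours the rank test. If both arms have SD 2.55 and the active mean is low, Mann-Whitney U is the more powerful (0.83 vs 0.80 at 5.71 vs 3.71; 0.93 vs 0.80 at 4 vs 2). That is a reason to keep it as a sensitivity analysis. The means test still delivers the 80% the trial was sized for.

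**Conclusion.** The point holds as one of estimation and prespecification. The plan sizes the trial on a mean difference, lets a normality test decide whether means are reported at all, and names no effect estimate or interval on either route. These facts are in the text and need no assumption.

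The size of the problem does rest on assumptions. Over the four tabulated scenarios at 27 per arm, the chance of losing the mean summary runs from about a third to about four fifths, and it is lower still if counts are high and less variable than Poisson. An informal contrast of medians would carry about 1.8 to 1.9 times the variance of the mean difference. The sample size of 68 is not in question. The sponsor should make the change, but the trial's test would remain valid without it.

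**What to change.** In the SAP (Statistical method) and the matching Protocol section, remove the primary endpoint from the normality rule and insert:

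*The primary analysis compares mean 12-month RTI counts between arms with an unequal-variance (Welch) test, reported as the difference in means with 95% CI, whatever the Shapiro-Wilk result. Mann-Whitney U is a sensitivity analysis.*

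A count-model rate ratio with 95% CI, named in advance, would also be acceptable. It would move the answer off the scale used for sizing, so the plan should say so. What matters is one named estimate with its interval.

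Do the same for the count-type secondary endpoints (antibiotic cycles and days, missed school or work days); bootstrap intervals would suit these. Correct the wording that has Mann-Whitney U comparing means. If the normality rule stays for other variables, state whether it is applied by arm, pooled or to residuals.

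The cost is one paragraph, with no new data, no change in sample size and no loss of the planned 80% power. In return the report would carry an interval of about ±1.4 RTIs at 27 per arm, or ±1.2 at 34.

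### Adenoid size is recorded at baseline and four follow-up visits with dropout allowed for, but the SAP's only stated between-arm method for continuous variables is an unadjusted two-group test, so a 12-month comparison would leave leavers' earlier values unused and can be biased.

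*SAP*

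**What the plan says.** The protocol's secondary endpoints include "Size of adenoid tissue over the 12 months according to" radiography and flexible nasopharyngoscopy. Under Procedures, children are measured at entry and return every 3 months, when "they will be evaluated by the ENT specialist for the adenoid tissue size". The first-visit form (Appendix 1, Table 1) has fields for the radiographic AC/SP ratio and the percent choanal obstruction. The follow-up form (Table 5), headed "Visit (3-6-9-12 months", has the same two fields. Each child can therefore have five values per instrument.

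In the SAP's Statistical method section, ANOVA or Mann-Whitney U "statistics will be used to compare means between both treatment groups for continuous variables". Categorical variables get a chi-square test. A Bonferroni procedure is named for the paired intervals 0 to 3 and 0 to 6 months. The SAP names no repeated-measures model, baseline adjustment, analysis set, missing-data rule or time point for the adenoid comparison. Dropout appears only in the sample size paragraph: "assuming a drop-rate of 20% after 6 months".

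**The concern.** A two-group test needs one value from each child. If that value is the month-12 size, a child who leaves after month 6 has no place in the test, although that child's first half-year was measured. Two things are at stake.

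The first is precision. Earlier sizes carry information about the missing month-12 size, and baseline size would explain some of the variation between children. The stated test uses neither.

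The second is bias. Children whose adenoids stay large may be likelier to leave. If this removes more of the large adenoids from the placebo arm than from the OM-85 arm, the remaining placebo children look better than their arm really is, and an OM-85 effect is understated. The opposite pattern would overstate it. Adenoid size is in the trial's title and research question, so the result will be read closely even though it is secondary.

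**Working it through.** **1. The plan's own figures.** The SAP states: "A sample size of 54 randomized patients (27 per group) will provide at least 80% power". The target is a difference of 2.0 RTIs, with SD 2.55. Alpha follows from "All P values are 2-tailed; a P value of less than .05 are considered statistically significant".
- Normal approximation: n = 2(1.96 + 0.842)² x 2.55² / 2² = 25.5, so 26 per arm. With the t distribution, power is 79.2% at 26 and 80.7% at 27, so 27 is right.
- Inflation: 27 / 0.8 = 33.75, so 34 per arm and 68 in all.
- These figures concern RTIs and reproduce.

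**2. Values left unused.** Allowed-for leavers: 68 - 54 = 14 (20% of 68 is 13.6). If all leave after the month-6 visit, each has sizes at months 0, 3 and 6: 14 x 3 = 42 per instrument, of 68 x 5 = 340 planned.

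**3. Assumptions for the rest.** The documents give no SD, correlation, effect or dropout mechanism for adenoid size. Assumed: normal sizes at months 6 and 12 in SD units, larger meaning more obstruction (the AC/SP ratio runs the other way), and correlation ρ of 0.5 to 0.8. Positive bias works against OM-85. The comparison is between completers' month-12 means and an estimate that also uses month-6 values.

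**4. Random dropout.** With 27 of 34 per arm remaining, the variance ratio (using month 6 / completers only) is close to 1 - ρ² x 7/34 + (1 - ρ²)(7/34)/24.
- ρ = 0.5: 1 - 0.051 + 0.006 = 0.955.
- ρ = 0.8: 1 - 0.132 + 0.003 = 0.871.

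The gain is about 5 to 13% of variance. A 6,000-trial simulation gave 0.954 to 0.856, or 5 to 14%; the difference at the top is about what simulation error would produce. Baseline adjustment is not counted.

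**5. Size-related dropout.** If it acts on month-6 size, completer bias is ρ times the shift that dropout causes in the difference between arms in mean month-6 size.

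| Assumed pattern | Completer bias (SD) |
|---|---|
| Same rule in both arms, no treatment effect | about 0 |
| Same rule, true month-12 effect -0.5 SD | 0.02 to 0.07 |
| 10 placebo and 4 OM-85 leavers, likelier if larger | 0.09 to 0.13 |
| 20% per arm; size-related on placebo only, random on OM-85 | 0.11 to 0.18 |
| The 10 largest placebo adenoids leave, 4 OM-85 leavers random | 0.24 to 0.38 |

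The second and fourth rows use log-odds of leaving of 1.5 per SD of month-6 size. In the fourth, the placebo stayers' mean shifts by about 0.226 SD: 0.5 x 0.226 = 0.11 and 0.8 x 0.226 = 0.18. In the last row, the mean of the lowest 24/34 of a normal distribution is about -0.488 SD: 0.5 x 0.488 = 0.24 and 0.8 x 0.488 = 0.39, slightly less in samples of 34.

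For scale, the standard error with 24 and 30 completers is √(1/24 + 1/30) = 0.27 SD.

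**6. After conditioning on month 6.** Bias is about zero (within 0.005 SD) in every row. That follows from the set-up, in which dropout depends only on recorded size. If dropout on placebo depended instead on the unrecorded month-12 size, with the same 0.226 SD shift, conditioning would leave at least 0.226(1 - ρ²): 0.17 SD at ρ = 0.5 and 0.08 SD at ρ = 0.8.

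**The case against.** The strongest reply is that the SAP is loosely written rather than wrong. A reader might infer that it discards leavers' data and that the 12-month adenoid result will therefore be biased. The documents do not support that.
- The SAP sets neither a month-12 nor a completers-only adenoid test. With no missing-data rule, carrying the last value forward would be equally open.
- The 0 to 3 and 0 to 6 month comparisons may use leavers' early values. ANOVA with Bonferroni on paired intervals could even mean a repeated-measures ANOVA.
- The two-group test is the only between-arm method for continuous variables, not the only one: Appendix 3 grades the AC/SP ratio 0 to 3, which could go to chi-square.
- No passage suggests that dropout will differ by arm, and the worst case is deterministic. The 0.09 to 0.13 SD case is a third to a half of one standard error, and 5 to 13% of variance is about 2 to 7% of standard error.
- The dropout wording may mean 20% lost by month 6, in which case leavers have fewer values and the gain shrinks.

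All of this stands as a limit on the claim. It does not remove the point. The interval comparisons stop at month 6, and the SAP does not say whether they are within or between arms, so they cannot give a 12-month arm difference. A conventional repeated-measures ANOVA needs complete records and would also drop leavers. An open missing-data rule means that the choice could be made after the data are seen. Size-related leaving is plausible, since the protocol describes adenoid hypertrophy as often ending in surgery and makes surgery need an endpoint.

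**Conclusion.** The point holds in a conditional form. For an endpoint measured five times, with dropout expected, the stated between-arm method as normally applied uses one value per child and no baseline. A better method is available on data already planned.

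The loss of precision is modest: about 5 to 13% of variance, if dropout is random and ρ is 0.5 to 0.8. Material bias needs dropout that depends on size and also differs by arm: about 0.1 to 0.2 SD under moderate mechanisms, with 0.24 to 0.38 SD as an upper bound. A treatment effect on size under one common rule gives only 0.02 to 0.07 SD, and with no effect about zero. All of these rest on assumed correlations and mechanisms.

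This should be changed, but it concerns a secondary endpoint. The primary RTI analysis and the 68-child sample size are unaffected.

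**What to change.** In the SAP:
- Analyse each adenoid measure with a linear mixed model for repeated measures, using all recorded values at months 3, 6, 9 and 12 from every randomised child. Include arm, visit, arm by visit and baseline size, with an unstructured covariance. Report the month-12 arm difference with its 95% CI.
- Keep the two-group ANOVA or Mann-Whitney U on completers as a sensitivity analysis. This also gives a check that does not rely on normality.
- State how sizes recorded after adenoid surgery enter the analysis. Otherwise the model's answer for those children is left undefined.
- Add a sensitivity analysis for dropout that depends on unrecorded size, for example by shifting the values assumed for leavers by a range of amounts in each arm.
- Say whether the 20% dropout is expected by month 6 or after it.

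The cost is SAP wording and a little more analysis; no new data are needed. The sponsor should confirm that the named software version can fit the model. The downsides are an approximate-normality assumption for a ratio with a floor at 0 and for a perceived percentage, and the assumption that dropout depends only on recorded values. The second is weaker than what the completer comparison needs, but it cannot be verified from the data.
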